# Introduction

This document is a protocol for a human research study. This study is to be conducted according to US and international standards of Good Clinical Practice (FDA Title 21 part 312 and International Conference on Harmonization guidelines), applicable government regulations and Institutional research policies and procedures.

#### **Background**

This proposal focuses on the novel use of high-intensity interval training (HIIT) as a method to improve physical function in patients with symptomatic knee osteoarthritis (OA).

Knee OA is one of the top five causes of disability in the United States.¹ The estimated lifetime risk of symptomatic knee OA is nearly 45% by 85 years of age, and this risk grows to 60% among those who are obese.² Physical activity reduces pain and increases physical function in people with knee OA and is a mainstay for treatment of OA.³-7 The Department of Health and Human Services (DHHS) guidelines support ≥150 minutes of moderate-to-vigorous physical activity per week for improved health and weight management, but less than 10% of adults and few people with symptomatic knee OA achieve these recommended levels.¹0,¹¹¹ Lack of time and motivation are common reasons for not maintaining regular physical activity.¹² Furthermore, many people with OA are unable to complete the DHHS recommended duration of moderate intensity aerobic exercise because of pain levels or functional limitations. Given the current high rates of inactivity in symptomatic knee OA patients, novel approaches are needed to help individuals achieve physical activity levels that will result in reduced disability.

High-intensity interval training (HIIT) is a time-efficient exercise strategy in which short intense exercise periods are interspersed with recovery periods. HIIT requires as little as 10 minutes of exercise per session and results in improved health and physical function, often in as few as 2 weeks. 13 This form of exercise requires less frequent and shorter duration exercise (e.g., 2 times per week for 10 minutes) than either traditional long duration low-moderate intensity exercise or high intensity resistance (strength) training. HIIT is safe in a variety of clinical populations including patients with heart failure, 14 stroke, 15 cancer, 16 and chronic obstructive pulmonary disease,  with high tolerability and few adverse events. Importantly, HIIT programs are highly adaptable, accommodating individual limitations to minimize pain and joint impact, and maximize comfort. Recently, the need for more data on higher intensity exercise in OA patients has been highlighted.  To date, research examining HIIT among people with OA is sparse, with only 1 previous study showing benefits of a 6week combined aquatic treadmill walking and balance program on joint pain, balance and function.  Longer term data are needed on a HIIT program tailored to a patient's access to and comfort with exercise equipment. Our preliminary evidence suggests that HIIT is a promising approach for maximizing physical activity among people with knee OA because it allows for short exercise bouts with rest periods (which may be more feasible for people with knee OA), yet results in comparable or greater benefits to traditional, continuous moderate intensity exercise. 22, 23 Furthermore, HIIT dramatically improves muscle strength and body composition within three weeks.  two risk factors for progression of knee OA symptoms.

## **Study Aims**

For this feasibility and proof-of-concept study, we will conduct a HIIT intervention for people with knee OA (40-75 years old) and obtain preliminary data on changes in outcomes during and after HIIT. A protocol previously evaluated by our research group will be implemented under the supervision of trained research personnel 2 times per week for 12 weeks. An acute evaluation (week 6) will occur to better understand the feasibility of the intervention in 30 participants with symptomatic knee OA for the primary outcomes of performance-based physical function and knee OA symptomatic burden (pain), along with secondary outcomes of balance, isometric knee extensor and flexor strength (factors associated with physical function and symptomatic knee OA progression), cardiorespiratory fitness, and body composition.

**Aim 1.** To examine the feasibility and acceptability of the HIIT program in patients with knee OA symptoms ranging from mild to severe. We will determine adherence to and tolerability of HIIT, acceptability, and recruitment and retention rates of patients through 6- and 12-week assessments.

**Aim 2.** To determine short-term changes in outcomes among patients with symptomatic knee OA participating in a HIIT intervention. Hypothesis: Patients with knee OA will have clinically important improvements in physical function, knee OA symptomatic burden (pain), balance, isometric knee extensor and flexor strength, cardiorespiratory fitness, and body composition after completing HIIT for 6 weeks and 12 weeks, respectively.

# **Study Protocol**

This project is a single-arm feasibility and proof-of-concept study in which all participants will receive 12 weeks of HIIT. All patients will undergo a series of baseline (week 0), mid- (week 6), and post-intervention (week 12) evaluations, as described below. Baseline values for all measures will be collected within the 10 days prior to initiation of the intervention. Testing will occur at 6 weeks (± 5 days) and 12 weeks (± 5 days). Testing at 6 weeks is included due to the rapid results often reported after as little as 2 weeks of HIIT. This testing point will more fully inform the development of a larger scale trial and the appropriate duration of HIIT for a knee OA population, as well as allow for modification of intensity to maintain sufficient training intensity. All

training will be performed in the Applied Physiology Laboratory or Campus Recreation Center on the UNC campus, with one-on-one supervision from trained research personnel, 2 times per week for 12 weeks. The project timeline is shown below.

# **Project Timeline (2 years)**

			Year					
Activity	1			2				
Quarter	1	2	3	4	1	2	3	4
Training and IRB approvals								
Informed Consent and Cardiovascular health screening								
Baseline Assessments								
6 week Assessments								
12 week Assessments								
Data Analysis, Abstract & Manuscript Preparation. Development of larger grant								

Tolerability, Feasibility, Compliance and Adherence (Aim 1). We will determine the percent of participants that screen into the study versus those approached and the percent of participants retained at the 6- and 12-week post-tests. Frequency and reasons for initial refusal, ineligibility, and drop out will be collected. Adherence and tolerability will be evaluated based on number of sessions attended/completed, modifications, such as change in mode; number of training days per week; recovery days needed between sessions to complete training, and severity of pain on a scale of 0-10 (no pain-extreme pain) during and after exercise as a measure of tolerability. The physical activity enjoyment scale will be given to assess participant enjoyment of exercise on each training day.

Outcomes (Aim 2). Because HIIT in people with knee OA is novel, a set of functional, symptomatic, and physiological variables will be included as outcomes. These outcomes will allow for the monitoring of initial changes related to the intervention and to identify the most appropriate measures for inclusion in a larger trial.

*Physical Function* will be measured with performance based tests: 40 m fast-paced walk test, 30-s chair stand test, a stair-climb test, and Timed Up and Go Test. All physical function tests are in accordance with the Osteoarthritis Research Society International recommendations.

Knee OA Symptomatic Burden. Participants will be asked to complete the Knee Injury and Osteoarthritis Outcome Score (KOOS). The KOOS questionnaire was developed to assess the patient's opinion about his or her knee and associated problems. It is widely used for research purposes in clinical trials of knee OA, and its psychometric properties have been confirmed. The KOOS is available online for free use. An advantage of the KOOS is that it includes the Western Ontario & McMaster Universities Osteoarthritis Index (WOMAC). The WOMAC, a measure of lower extremity pain (5 items), stiffness (2 items), and function (17 items), will be used to measure overall symptomatic burden of OA. All items are rated on a Likert scale of 0 (no symptoms) to 4 (extreme symptoms). The reliability and validity of the WOMAC total score and subscales have been confirmed, and this scale has been widely used in trials of behavioral interventions for patients with knee OA, confirming its sensitivity to change. The total WOMAC score will be assessed, as well as the pain and function subscales.

Balance will be evaluated with the single leg stance and side-by-side, semi-tandem, and tandem tests.

*Muscle Strength*. A Humac isokinetic dynamometer will be used to measure isokinetic power and isometric strength of knee flexors and extensors. Measures will be assessed according to manufacturer's instructions, with the primary assessment of power at 60 degrees per second and for strength at 60 degrees of knee flexion. These selections are based on clinical relevance and that persons with OA exhibit high correlations (r>0.7) for assessments of power at varying speeds and of isometric strength at varying angles.

Cardiorespiratory fitness, measured by peak oxygen consumption (VO2peak), is the gold standard for identifying fitness level and evaluating cardiovascular effects. This test will be used to establish individual training intensity. All participants will perform a ramp based cycling ergometer test with respiratory gases continuously monitored with open-circuit spirometry using a calibrated metabolic cart (True One 2400®, Parvo-Medics, Inc., Provo, UT). Data will be averaged over 15-second intervals, with the highest 15-second oxygen consumption, minute ventilation and heart rate recorded as the peak oxygen consumption (VO2peak), time to exhaustion, and maximum heart rate, respectively. In accordance with the Exercise and Sport Science Institutional Review Board Standard Operating Procedures (EXSS-IRB SOP), following a 12 lead electrocardiogram (EKG) cleared by a study physician, 3 trained research personnel (for safety purposes per IRB procedures) will perform cardiorespiratory fitness testing.

Body composition will be assessed to evaluate the effects of HIIT on fat mass, lean body mass, and visceral fat. Previous data demonstrated positive effects of HIIT on fat mass, visceral fat, and, more importantly for this OA population, lean mass. Dual energy x-ray absorptiometry (DXA; GE Lunar iDXA, Software version 16, Chicago IL) will be used to determine whole-body fat mass, lean mass, bone mineral density, and segmental (arms, legs) body composition. Each scan will be performed by the same certified DXA technician, and previous data from this lab indicate high test-retest reliability for fat mass (intraclass correlation coefficient [ICC]=0.98, standard error of measurement [SEM]=0.85 kg), and lean mass (ICC=0.99, SEM=1.07 kg). In accordance with the EXSS-IRB SOP, personnel trained with radiation exposure training will complete the DXA scans.

[figure not shown]
*HIIT Intervention:* All training will be performed in the Applied Physiology Laboratory or Campus Recreation Center on the UNC campus, with one-on-one supervision from trained research personnel, 2 times per week for 12 weeks. Details are described below and in Figure 3.

- Type: Mode of exercise will vary based on participant limitations and choice, including activities such as walking, biking, elliptical machine, and swimming, with individual mode being consistently maintained whenever possible throughout the duration of the study. Cycling will be suggested as the primary mode, but another mode will be selected if cycling is not feasible. If limitations arise for the participant during familiarization and throughout the study (i.e. discomfort, inability to increase heart rate), training mode will be modified, and noted, to inform feasibility components (Aim 1).
- Intensity: Individualized training intensity for each participant will be established from baseline cardiovascular fitness (VO2peak) testing. Baseline maximal oxygen consumption testing and maximum workload will be used to determine the intensity of each exercise bout (90% of maximum heart rate obtained during testing).
- Session: Each training session will consist of a 3-5 minute warm-up, followed by 10 repetitions of 1-minute bouts at individualized training intensity with 1-minute rest periods. We anticipate that most participants in this study will be able to complete all 10 1-minute bouts during the first session, based on our prior experience of HIIT in people with other diseases who have low levels of physical activity at baseline. Individuals who are

unable to achieve this protocol in initial sessions will be encouraged to complete all 10 bouts for as long as possible each bout. If they cannot finish the entire minute, the 1-minute rest period will begin as soon as they stop, followed by the next bout. Intensity will be re-established and adjusted following the 6-week testing. Sessions will take place twice per week, with at least 24 hours in between training sessions.

Structured Interview. A structured one-on-one interview will occur with participants after completion of the HIIT program. The interview will be used to learn about barriers and concerns they experienced with regard to the current training protocol; preference of exercise mode and instruction; and opinions on what information participants would find helpful to transition to an at-home and or independent program. While we do not intend to formally analyze the interview responses, we do anticipate that they will be useful for refining our intervention program for inclusion and development of a home-based component for future trials.

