Three participants per month are expected to be enrolled with at least 80% retention during the study period. As part of Aim 1, adherence to and tolerability of HIIT, acceptability, and recruitment and retention rates of patients through 6- and 12-week assessments will be determined. This will be determined as the percent of participants that screen into the study versus those approached and the percent of participants retained at the 6- and 12-week post-tests. Frequency and reasons for initial refusal, ineligibility, and drop out will be collected. Adherence and tolerability will be evaluated based on number of sessions attended/completed, modifications, such as change in mode; number of training days per week; recovery days needed between sessions to complete training, and severity of pain on a scale of 0-10 (no pain-extreme pain) during and after exercise as a measure of tolerability. If the HIIT intervention is shown to be well-tolerated and promising, results of this preliminary study will lay the foundation for a large randomized controlled trial to establish the efficacy of HIIT as a revolutionary approach for enhancing the rehabilitation and management of knee OA.

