# **Eligibility Criteria**

All participants must meet the following criteria:

- Between the ages of 40 and 75 years old
- Body mass index of 18.5-50 kg/m^2
- Exhibits symptomatic knee OA, defined as a diagnosis of knee OA, as identified from UNC electronic medical records, and current knee symptoms in at least one knee, having a minimum score of 6 out of 20 on the Western Ontario and McMasters Universities Osteoarthritis Index (WOMAC) pain subscale.

Potential participants meeting any of the following criteria (based on the electronic medical record or in laboratory screening) will be excluded if:

- Individuals diagnosed with a cardiovascular condition restricting exercise
- Individuals currently meeting Department of Health and Human Services Guidelines for physical Activity (≥ 150 minutes per week)
- Individuals currently doing HIIT
- Individuals currently participating in physical therapy for knee OA
- Individuals currently participating in another OA intervention study
- Received a corticosteroid or hyaluronic acid intra-articular injection involved in the knee in the previous 3 weeks or scheduled for during the intervention
- Diagnosis of gout in the knee
- Diagnosis of Rheumatoid arthritis
- Diagnosis of Fibromyalgia
- Other systemic rheumatic disease
- Severe dementia or other memory loss

- Active diagnosis of psychosis or uncontrolled substance abuse disorder
- Hospitalization for a stroke, heart attack, or heart failure, or had surgery for blocked arteries in the past 3 months
- Total joint replacement knee surgery, other knee surgery, meniscus tear, or ACL tear in the past 6 months
- On a waiting list for total joint replacement
- Severely impaired hearing or speech
- Pregnant or planning to become pregnant while enrolled in the study
- Inability to speak English
- Serious or terminal illness as indicated by referral to hospice or palliative care
- Nursing home residence
- Inability to ride a stationary bike
- Any other health problems that would prohibit safe participation in the study.

Use and changes of medications for OA will be monitored and recorded during the study but will not be a reason for exclusion. Participants will be withdrawn if they develop any new health problems or other events that would either a) make participation in the study intervention or measures unsafe or b) confound study outcomes. These largely mirror study exclusion criteria and are as follows:

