# Participant Evaluations and Follow-up

### **Timeline and Visit Schedule**

The current study consists of 27 total visits: 3 testing visits and 24 training sessions. All visits will take place at the Applied Physiology Laboratory and/or the Student Recreation Center. The three testing visits will consist of assessments of physical function, cardiorespiratory fitness, body composition, balance, symptoms, and muscular strength. These visits will occur at baseline, 6-weeks, and 12 weeks. The HIIT intervention will occur over the course of 24 separate training sessions, occurring two times per week for two 6-week sessions.

Week	Visit	Testing	Training	Measures Collected
	#			
0	1	X		
 
Physical function: 40 m fast-paced walk test, 30-s chairstand test, a stair-climb test, and Timed Up and Go Test
 
Knee OA Symptomatic Burden: WOMAC
 
Balance: single leg stance and side-by-side, semi-tandem, and tandem tests
 
Muscle Strength. isokinetic dynamometer for power at 60 degrees per second and for strength at 60 degrees of knee flexion.
 
Cardiorespiratory fitness: peak oxygen consumption (VO2peak)
 

				Body composition: DXA for fat mass, lean body mass, and visceral fat
1-5	2-11		X	
 
Heart rate: chest strap heart rate monitors to identify heart rate and intensity during each training bout
 
Ratings of perceived exertion: Borg perceived exertion scale
 
Severity of pain: visual analog scale of 0-10 (no pain-extreme pain) during and after exercise
 
Training bouts completed
 
Mode of exercise
 
Exercise enjoyment
 

6	12	X		
 
Physical function: 40 m fast-paced walk test, 30-s chairstand test, a stair-climb test, and Timed Up and Go Test
 
Knee OA Symptomatic Burden: WOMAC
 
Balance: single leg stance and side-by-side, semi-tandem, and tandem tests
 
Muscle Strength. isokinetic dynamometer for power at 60 degrees per second and for strength at 60 degrees of knee flexion.
 
Cardiorespiratory fitness: peak oxygen consumption (VO2peak)
 
Body composition: DXA for fat mass, lean body mass, and visceral fat
 

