# **Statistical Considerations**

## Aim 1 Analyses

Analyses will be primarily descriptive and will include data from all participants during their experience using HIIT. First, the flow of participants through the study (i.e., screened, recruitment, enrollment [along with refusals and ineligibility, with reasons], and follow-up at each time point) will be descriptively summarized using frequencies and proportions. Then, compliance and tolerability of HIIT (i.e., proportion of sessions completed, change in mode, number of training days per week, recovery days between sessions), along with 95% confidence intervals, will be summarized. We will also descriptively summarize pain on a 0-10 scale, during and after exercise, as well as participant enjoyment of exercise by training day, and will use informative graphical approaches where useful.

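### Session pain is rated only during and after exercise, so raw levels cannot separate pain provoked by HIIT from that day's existing OA pain

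*Combined protocol and SAP*

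**What the plan says.** The Aim 1 paragraph under Project Timeline lists, after attendance, modifications, training days and recovery days, "severity of pain on a scale of 0-10 (no pain-extreme pain) during and after exercise as a measure of tolerability". The section Retention: Role of All Study Personnel repeats this. In Timeline and Visit Schedule, the rows for training weeks 1-5 and 7-12 both give "Severity of pain: visual analog scale of 0-10 (no pain-extreme pain) during and after exercise". The analysis text under Aim 1 Analyses follows suit: "We will also descriptively summarize pain on a 0-10 scale, during and after exercise".

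The other relevant statements are these:

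- **Entry.** Eligibility Criteria requires symptomatic knee OA, "having a minimum score of 6 out of 20 on the Western Ontario and McMasters Universities Osteoarthritis Index (WOMAC) pain subscale".
- **Other pain measure.** The outcomes text says "The total WOMAC score will be assessed, as well as the pain and function subscales". The visit table places the WOMAC at the three testing visits only.
- **Design.** Study Protocol states: "This project is a single-arm feasibility and proof-of-concept study in which all participants will receive 12 weeks of HIIT".
- **Expected course.** The Aim 2 hypothesis under Study Aims is that knee pain, among other outcomes, will improve by weeks 6 and 12.
- **Medication.** Eligibility Criteria and Concomitant Medications allow OA medication to change and have the changes recorded.

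**The concern.** A rating made during or just after a bout reflects two things: the pain the participant arrived with and whatever the session added. The first is never recorded at a session, and no comparator group supplies it indirectly. A participant having a bad knee day can look like someone who tolerates HIIT poorly. If background pain falls over 12 weeks, as Aim 2 predicts, or is reduced by a change in analgesics, session ratings may fall and look like growing tolerance even when each session provokes the same pain. Training intensity is also reset after the week 6 tests, so the later ratings mix a possible change in background pain with a changed stimulus.

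This rating is the only direct measure of pain at the training sessions. The study is meant to inform a larger trial, and the plan allows the exercise mode to change because of discomfort. The pain provoked by a session is therefore useful information, and it cannot be reconstructed later if the starting level was not recorded.

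**Working it through.** The plan gives no figure to reproduce here. The check is of timing first, and then of what the planned ratings can identify.

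**1. Timing in each place that describes the rating**

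| Place | During | After | Before |
|---|---|---|---|
| Project Timeline, Aim 1 paragraph | yes | yes | no |
| Retention: Role of All Study Personnel | yes | yes | no |
| Visit table, weeks 1-5 | yes | yes | no |
| Visit table, weeks 7-12 | yes | yes | no |
| Aim 1 Analyses | yes | yes | no |

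The week 0 list in the visit table contains the WOMAC but not the 0-10 scale. The five places agree, so this is the plan's design and not a slip in one section.

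**2. What the ratings identify**

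For one session let P be pain before the warm-up, d the change by the time of the during rating, and a the change by the time of the after rating.

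- During = P + d
- After = P + a
- After minus during = a - d

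P cancels in the last line, but what remains shows only whether pain eases once exercise stops. Two observed values cannot give three unknowns, so neither d nor a can be recovered.

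**3. One session (assumed values)**

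A during rating of 4 arises from 4 + 0, 3 + 1, 2 + 2 or 0 + 4. The rise from exercise is 0, 1, 2 or 4 points, and the planned data are the same in each case.

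**4. Trend over the programme (assumed values)**

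- Early: P = 4, d = 2, so the during rating is 6.
- Late: P = 2, d = 2, so the during rating is 4.
- Reported fall: 2/6 = 33%. Change in provoked pain: 0.

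**5. Entry criterion**

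6/20 = 30% of the WOMAC pain range. Mapped linearly to 0-10, which is an assumption that the documents do not make, this is about 3. The subscale has five items scored 0-4, so a total of 6 can come from two items (4 + 2). It shows pain at screening, not a level just before any given session.

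**6. Precision of a change score**

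If ratings before and during have the same SD s and correlation r, the SD of the change is s × √(2(1 - r)). I take 27 participants (30 less the 10% loss assumed under Power and Sample Size), one value each, and assume s and r because the plan gives neither. The 95% half-widths (t with 26 df) are:

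| s | Raw level | Change, r = 0.3 | Change, r = 0.5 | Change, r = 0.7 |
|---|---|---|---|---|
| 2.0 | 0.79 | 0.94 | 0.79 | 0.61 |
| 2.5 | 0.99 | 1.17 | 0.99 | 0.77 |

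Over this range the change is estimated about as precisely as the level: somewhat less so if r is below 0.5, and more so if it is above.

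**The case against.** The strongest reply is that the raw level is a legitimate tolerability measure. Whether patients can exercise at the pain they actually feel is a fair feasibility question, and the plan does not claim to estimate pain caused by HIIT. That stands: within-session change answers a further question, and its absence does not make the level worthless.

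Second, background drift is partly visible. WOMAC pain is collected at the testing visits, and medication changes are recorded, summarised and to be considered in interpretation. This also stands, but only coarsely: three time points on a different scale cannot serve as a same-day baseline.

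Third, Study Protocol says "Baseline values for all measures will be collected within the 10 days prior to initiation of the intervention", which might seem to cover this scale. It does not fill the gap. The week 0 list omits the rating, and a single value up to 10 days old could not be the baseline for 24 sessions over 12 weeks.

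Fourth, delayed pain is not wholly missed. Recovery days needed between sessions reflect it indirectly, and the adverse event grading gives passing muscle soreness as its example of a mild event. That stands.

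A reader might infer that pain is the main tolerability measure, or that it triggers the next trial, because of the sentence that begins "If the HIIT intervention is shown to be well-tolerated and promising, results of this preliminary study will lay the foundation for a large randomized controlled". The documents do not support this. Aim 1 Analyses names completed sessions, mode changes, training days and recovery days as compliance and tolerability, and adds pain afterwards as a further descriptive summary. No pain threshold or decision rule is set anywhere.

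**Conclusion.** The point holds for the session pain rating. As scheduled, it cannot separate pain provoked by a session from the OA pain already present, and a downward trend could reflect lower background pain. This rests on the agreed timing in all five places and on the single-arm design; it does not depend on the illustrative numbers.

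The size of any distortion in this trial is unknown. The 4-point and 6-to-4 examples use assumed values and show what is possible, not what is expected.

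Two stronger conclusions should not be drawn. The tolerability assessment as a whole is not uninterpretable, because attendance, mode changes, recovery days, bouts completed and adverse events need no pre-session rating. Nor does the entry score prove that every participant arrives at every session in pain; that uncertainty is a reason to measure it. The change is a cheap improvement to one descriptive component of a 30-person feasibility study.

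**What to change.** - **Measurement.** In the Aim 1 paragraph under Project Timeline, in Retention: Role of All Study Personnel, and in both training rows of the visit table, add the same 0-10 rating before the warm-up of each session. Word it for the knee, identically at all three times.
- **Analysis.** In Aim 1 Analyses, summarise within-session change (during minus before, after minus before) alongside the raw levels.
- **Delayed worsening.** Describe the pre-session ratings over successive sessions as a partial check only, and say that day-to-day variation in OA pain also affects them.

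The cost is one extra question per session, up to 24 per participant, on a form already completed under one-to-one supervision, plus a short addition to the analysis text. The exercise programme and the visit schedule do not change.
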